## 1 Introduction

### 1.1 Background

Neovascular age-related macular degeneration (nAMD) is characterized by the presence of choroidal neovascularization (CNV). Choroidal neovascularization consists of abnormal blood vessels originating from the choroid and can lead to hemorrhage, fluid exudation, and fibrosis, resulting in photoreceptor damage and vision loss.

Vascular endothelial growth factor (VEGF) has been shown to be elevated in patients with nAMD and is thought to play a key role in the neovascularization process ([Spilsbury et al 2000](#)). Anti-vascular endothelial growth factor (anti-VEGF) treatments, such as ranibizumab (Lucentis®) and aflibercept (Eylea®) have been demonstrated to improve visual acuity in patients with nAMD in multiple clinical trials.

Brolucizumab is a new generation of anti-VEGF. Brolucizumab is the first humanized single-chain antibody fragment (scFv), which inhibits vascular endothelial growth factor A (VEGF-A). The safety and efficacy of brolucizumab were assessed in 2 randomized, multicenter, double-masked, active treatment-controlled Phase 3 studies in nAMD patients (the HAWK study (RTH258-C001 [NCT02307682]) and the HARRIER study (RTH258-C002 [NCT02434328]) comparing brolucizumab every 12 weeks (q12w) or every 8 weeks (q8w) to aflibercept q8w according to its approved label.

In these studies, patients in both treatment arms received 3 loading doses every 4 weeks (Day 0, Week 4 and Week 8), followed by an q12w/q8w maintenance regimen for brolucizumab 6 mg arm and an q8w maintenance regimen for the aflibercept 2 mg arm. For the q12w/q8w treatment regimen, q12w/q8w treatment frequencies were allocated according to patient's individual treatment need based on disease activity assessments performed by the investigator at pre-specified visits. Within the q12w/q8w regimen, the initial treatment schedule after the loading phase was q12w. If disease activity was identified by the investigator in brolucizumab-treated patients at any of the disease activity assessments, dosing was adjusted to q8w (i.e. "q12w/q8w regimen"). Once patients were adjusted to a q8w interval, they stayed on that interval until the end of the study (Week 96/Exit).

Brolucizumab met the primary endpoint of non-inferiority in change in best-corrected visual acuity (BCVA) from Baseline to Week 48 vs. aflibercept and achieved pre-specified superior anatomic outcomes vs. aflibercept for the following: mean change from Baseline in central sub-field retinal thickness (CSFT); percentage of patients with intraretinal fluid and/or subretinal fluid; percentage of patients with subretinal pigment epithelium (sub-RPE) fluid; and percentage of patients with no disease activity. The anatomical changes were evaluated with spectral domain-optical coherence tomography (SD-OCT) systems. As SD-OCT is not able to define the vascular network of CNV, the diagnosis of active CNV via SD-OCT relies on indirect parameters including assessment of the presence of subretinal or intraretinal fluid that is not specific to CNV.

Since the first global marketing authorization approval in the US, in Oct-2019, for the treatment of nAMD, adverse events (AEs) of intraocular inflammation (IOI), including retinal vasculitis and/or retinal vascular occlusion, that may result in severe vision loss, have been reported from post-marketing experience with brolucizumab (Beovu®). Results of the mechanistic study

BASICHR0049 of blood samples from nAMD patients exposed to brotacizumab and having subsequently developed Retinal Vasculitis (RV) and/or Retinal Vascular Occlusion (RO), taken together with accumulated data of the association of treatment-emergent immunogenicity and intraocular inflammation (IOI) indicate a causal link between the treatment-emergent immune reaction against brotacizumab and the brotacizumab-related “Intraocular inflammation, including retinal vasculitis and/or retinal vascular occlusion”. This finding supports the requirement to discontinue treatment with brotacizumab in patients who develop events of intraocular inflammation, including RV and/or RO.

These impacts on the risk/benefit balance of the product are considered to be low and the overall risk/benefit assessment remains positive, when patients who develop RV and/or RO are discontinued from further treatment with brotacizumab.

A new angiography tool, namely optical coherence tomography-angiography (OCT-A), was developed around 2010 to directly visualize retinal circulation ([Jia et al 2012](#)). OCT-A is a dye-less angiographic procedure based on split-spectrum-decorrelation-amplitude angiography. It enables the capture of scattered intra-vessel particles (mainly erythrocyte cells) at all levels of the retinal and inner-choroidal vasculature, thus providing 3-D imaging of the retinal circulation. OCT-A was not used for the HAWK and HARRIER studies.

OCT-A has since become an essential and widely used tool, particularly for imaging CNV and vascular diseases of the retina ([Mastropasqua et al 2015](#)). Follow-up of nAMD by means of OCT-A has been widely studied in recent years in the literature, describing OCT-A characteristics using both qualitative and quantitative criteria. A recent study ([Malamos et al 2017](#)) showed concordance between the changes demonstrated by B-scan OCT and the alterations of CNV flow morphology depicted by OCT-A in nAMD patients treated by anti-VEGF. Furthermore, several manuscripts have described OCT-A changes after anti-VEGF treatment.

The literature suggests that OCT-A is a good marker for assessing anti-VEGF therapeutic response, especially lesion size, which has been demonstrated to decrease under anti-VEGF therapy ([de Carlo et al 2015](#), [Miere et al 2017](#)). A 75% decrease in mean lesion area (SD: 21%) 1 month (29.6 days) after anti-VEGF injection in 17 naïve eyes with type 3 nAMD was reported in one study ([Phasukkijwatana et al 2017](#)). This remarkable response was associated with resolution of intraretinal and subretinal fluid on structural OCT in all cases. Similarly, another study ([Muakkassa et al 2015](#)) in CNV treatment-naïve patients (including patients with nAMD) reported a 23.6% mean decrease in greatest linear CNV dimension and 29.8% mean decrease in CNV area 4.8 weeks after initiation of a single anti-VEGF treatment.

Another study ([Coscas et al 2015](#)) reported on the response of patients with a mixed type I–II CNV to aflibercept therapy, with a reduction of the lesion area by 24% in the type II CNV component and by 11.3% in the type I CNV component at Week 12, 4 weeks after the last injection of a series of 3-monthly aflibercept injections. The anti-VEGF loading treatment effect in nAMD type I, type II and mixed CNV has been demonstrated in another study ([Miere et al 2018](#)) with a significant 65% decrease in CNV lesion area at Month 3, 4 weeks after the last loading phase injection in 13 naïve patients treated with anti-VEGF (from  $0.66 \pm 0.84 \text{ mm}^2$  at

Baseline to  $0.23 \pm 0.3 \text{ mm}^2$  at Month 3, Wilcoxon signed-rank test). This suggests that CNV lesion size might be a marker for assessing therapeutic response.

The long-term evolution of OCT-A features have been described in another study ([Miere et al 2017](#)) that reported a 21.6% decrease in CNV lesion area after a mean treatment duration of 11.7 months and 7.1 anti-VEGF treatments.

## **1.2 Purpose**

Considering the efficacy and safety findings demonstrated in the pivotal trials of brolucizumab, and the literature findings summarized above, this multicenter study of treatment-naïve nAMD patients is being performed to assess both early (at Week 12 just after loading phase) and long term (48 weeks [12 months]) effects of brolucizumab on CNV structure and activity.

## 2 Objectives and endpoints

**Table 2-1 Objectives and related endpoints**

Objectives	Endpoints
Primary objectives	Endpoints for primary objectives

 
To evaluate the short-term effect of brolucizumab on CNV lesion area as measured by OCT-A in nAMD patients.
 
	
 
Percentage change in CNV lesion area measured by OCT-A from Baseline to Week 12.
 

Secondary objectives	Endpoints for secondary objectives

 
To evaluate the long-term effects of brolucizumab on CNV morphology as measured by OCT-A in nAMD patients.
 
	
 
Percentage change in CNV lesion area measured by OCT-A from Baseline to Week 48.
 
Change in OCT-A features assessed by qualitative and quantitative criteria from Baseline by visit at Week 12 up to Week 48.
 

 
To evaluate the effect of brolucizumab on anatomical parameters as assessed by SD-OCT and FA from Week 12 up to Week 48.
 
	
 
Change in SD-OCT and FA features assessed by qualitative and quantitative criteria (e.g. (CSFT, sub- and/or intraretinal fluid, sub-RPE fluid) from Baseline by visit up to Week 48.
 

 
To evaluate the efficacy of brolucizumab up to Week 48 by assessing changes in BCVA.
 
	
 
Change in BCVA from Baseline up to Week 48.
 

 
To estimate the proportion of patients treated at q12w frequency with brolucizumab.
 
	
 
Proportion of patients who are maintained on an exclusive q12w interval following the loading phase through to Week 48.
 

 
To estimate the predictive value of the first q12w cycle for maintenance of q12w treatment with brolucizumab.
 
	
 
The probability of the first q12w interval for determining successful q12w maintenance at Week 48.
 


 
To evaluate the time from last IVT injection in the initiation phase to first visit with no disease activity.
 
	
 
Time from last IVT injection in the initiation phase to first visit with no disease activity.
 

 
To evaluate the safety of brolucizumab.
 
	
 
Incidence of AEs (serious and non-serious) reported in patients treated with brolucizumab.
 

AEs=adverse events, BCVA=best corrected visual acuity, CNV=choroidal neovascularization, CSFT=central sub-field retinal thickness, FA=fluorescein angiography, IVT=intravitreal, nAMD=neovascular age-related macular degeneration, OCT-A=optical coherence tomography-angiography, SD-OCT=spectral domain optical coherence tomography, sub-RPE=subretinal pigmented epithelium

### 3 Study design

This is a prospective, single-arm, open-label, multicenter study to evaluate the efficacy and safety of brolicizumab 6 mg in patients with nAMD.

Patients will be required to attend 6 mandatory study visits: Screening/Baseline Visit (Day 1), Week 4, Week 8, Week 12, Week 16 and Week 48 visits. The timing of the interim visits between Week 16 and Week 48 will depend on the patient’s injection regimen, i.e. q12w or q8w.

[figure not shown]
Patients who consent and meet all the inclusion and none of the exclusion criteria will be screened to evaluate eligibility. After confirmation of eligibility, patients will be included and treated with brolicizumab 6 mg.

Approximately 210 adult patients will be screened and included (10% drop-out rate and uninterpretable images at Baseline and Week 12 are expected) in France. The maximum study duration for 1 patient is 48 weeks, including Screening.

There will be 2 periods in this study (see [Figure 3-1](#)):

- Open-label treatment period: from Screening/Baseline (Day 1) to Week 40/Week 44 (depending on assigned regimen)
- Follow-up period: Week 40/Week 44 to Week 48

**Figure 3-1 Study design**

\* Week 40 or Week 44 according to treatment schedule

\*\* End of study visit: 4 or 8 weeks after the last IVT, depending on the last IVT date

### **Treatment period: Day 1 to Week 40/Week 44**

The Screening Visit and Baseline Visit (see [Table 8-1](#)) are the same visit.

One time re-assessment of patients is allowed, except for the purpose of capturing new BCVA or imaging assessments that previously failed to qualify the patient (except if image quality is poor and needs to be redone). As long as testing can be repeated within 14 days of the first screening, the other screening assessments do not need to be repeated. If rescreening is to occur beyond 14 days from the original Screening Visit date, then all screening procedures must be repeated. Medical judgment should be exercised to ensure that treatment of nAMD is not withheld in order for a patient to participate in the study.

After confirmation of eligibility, patients will be included in the study. A study visit schedule will be established at the time of Screening/Baseline Visit for all patients. All efforts should be made to adhere to the study visit schedule within a  $\pm 7$ -day window. For a given protocol visit, assessments can be performed on 2 consecutive days, provided both days are within the  $\pm 7$ -day window. Treatment (including at Screening/Baseline) is intended to be administered on the day of the study visit, or if this is not possible, within 3 days after the study visit when the per-protocol assessments will have taken place. If study visit assessments and the corresponding treatment occur on separate days, a repeat safety check-up should be performed prior to treatment of the eye and results documented in the source documents.

The Screening/Baseline Visit is defined as Screening/Baseline/Day 1. For all patients, the last potential study treatment will be at the Week 40 visit or at the Week 44 visit depending on whether patients receive the study treatment under the q8w or under the q12w schedule. The initiation phase starts on Day 1 and ends on Week 8. The q12w/q8w treatment regimen starts on Week 16 and ends on either Week 40 or Week 44 (see [Section 6.7.2](#)).

Patients will receive 3 initial doses every 4 weeks (Day 1, Week 4 and Week 8) (loading phase), which should be at least 21 days apart, followed by treatment q12w with the possibility of adjusting to treatment q8w based on disease activity. Disease activity will be assessed based on investigator's judgment of visual acuity and anatomical parameters as provided in the guidance to the investigators, e.g. decrease of visual acuity and/or other signs of the disease (e.g. intraretinal fluid (IRF), subretinal fluid (SRF), sub-retinal pigmented epithelium (sub-RPE) fluid, retinal hemorrhage, central retinal thickness (CRT) increase, etc.). Disease activity will be assessed during the first q12w interval at Week 16. If no disease activity is observed by the investigator in the study eye, disease activity will be assessed every 12 weeks (at Week 20, Week 32 and Week 44). If disease activity is observed by the investigator in the study eye at any of these visits, the study treatment will be adjusted by the investigator to a q8w treatment regimen and will remain on this regimen until Week 40/Week 44 (see [Section 6.7.2](#)). Patients who require study treatment every 4 weeks after the initiation phase will be discontinued from further study treatment at the next visit.

The mandatory study visits during the treatment phase are Day 1, Week 4 and Week 8 (assessment of CNV lesion evolution during initiation phase), Week 12 (primary endpoint), Week 16 (first time to reach disease activity criteria and first possible treatment) and Week 48 (last efficacy assessment) visits. The timing of the interim visits between Week 16 and Week 48 will depend on the patient's injection regimen, i.e. q12w or q8w. No visits are planned between the injection visits (see [Section 6.7.2](#)).

## **Post-treatment follow-up period: from Week 40/44 to Week 48**

For all patients completing the study as per protocol, the End of Study (EOS) assessment will be performed at Week 48, 4 weeks (for patients treated at Week 44) or 8 weeks (for patients treated at Week 40) ( $\pm 7$  days) following their last possible study treatment administration.

Patients withdrawn from the study prior to study completion will be asked to return for an EOS/Early Discontinuation Visit, 4 weeks ( $\pm 7$  days) following their last study treatment administration. For early treatment discontinuations (ETD) refer to [Section 9.1.1](#).

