 Intraocular pressure (IOP) will be assessed in the study eye, pre-dose and post-dose at every injection. The same method of tonometry has to be used through the whole study. Close monitoring of IOP should be performed by the investigator for any non-transient elevation in IOP ( $\geq 25$  mmHg). Intravitreal injection is not recommended unless normalization of the IOP has been achieved. Post-dose IOP should be assessed within 60 minutes after injection and if  $\geq 25$  mmHg, assessment should be repeated until back to normal. Monitoring of the optic nerve head perfusion after injection may be appropriate, at the discretion of the investigator. Results of these procedures will be recorded as appropriate in the source documents and if the findings constitute an AE, it should be recorded in the eCRF.

 Additional ophthalmic examinations and images will be performed in case of any signs of intraocular inflammation (IOI), retinal vasculitis, and/or retinal vascular occlusion.

 A telephone follow-up on safety should be performed one week after the first injection (a window for the phone call is +7 days). From the second injection onwards, similar phone calls should be made at investigator's discretion per local practice.

 The week 48 EOS assessments only apply to patients who completed the study per protocol. The assessments are not required for patients who have undergone ETD assessments and continued in the study without study treatment.

 ETD: Early treatment discontinuation applies to patients who discontinue early from study treatment and continue in the study. The assessments should be performed 4 weeks after the last injection of study drug. This can occur at any time point.

 For patients who continue in the study after ETD and up to Week 48 (end of study) while patient is on standard of care. Additional safety assessments and imaging can also be performed if required, as per investigators discretion. In addition, after ETD, subjects are not required to attend the mandatory visits at Week 12 and Week 48. The last visit should be at week 48. This can occur at any time point.

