  - Investigational treatment interrupted/withdrawn
  - Concomitant medication or non-drug therapy given
  - Patient hospitalized/patient's hospitalization prolonged (see [Section 10.1.2](#) for definition of SAE)
6. Its outcome:
  - Not recovered/not resolved
  - Recovered/resolved
  - Recovered/resolved with sequelae
  - Fatal or unknown.
7. Its location (ocular event / non ocular event)

Conditions that were already present at the time of informed consent should be recorded in the medical history of the patient.

Adverse events (including lab abnormalities that constitute AEs) should be described using a diagnosis whenever possible, rather than individual underlying signs and symptoms.

Adverse event monitoring should be continued until 30 days (safety follow-up) after the last administration of study treatment (see “Post-treatment follow-up period” in [Section 3](#)).

Once an AE is detected, it must be followed until its resolution or until it is judged to be permanent (e.g. continuing at the end of the study), and assessment must be made at each visit (or more frequently, if necessary) of any changes in severity, the suspected relationship to the interventions required to treat it, and the outcome.

Information about adverse drug reactions for the investigational drug can be found in the IB.

Abnormal test results constitute AEs only if they fulfill at least one of the following criteria:

- they induce clinical signs or symptoms
- they are considered clinically significant
- they require therapy

Clinically significant abnormal test results must be identified through a review of values outside of normal ranges/clinically notable ranges, significant changes from Baseline or the previous visit, or values which are considered to be non-typical in patients with the underlying disease. Investigators have the responsibility for managing the safety of individual patients and identifying AEs.

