### **10.1.3 SAE reporting**

To ensure patient safety, every SAE, regardless of causality, occurring after the patient has provided informed consent and until the last study visit or 30 days after the last administration of study treatment whichever is later must be reported to Novartis safety immediately, without undue delay, under no circumstances later than within 24 hours of learning of its occurrence. Detailed instructions regarding the submission process and requirements are to be found in the investigator folder provided to each site.

All follow-up information for the SAE including information on complications, progression of the initial SAE and recurrent episodes must be reported as follow-up to the original episode within 24 hours of the investigator receiving the follow-up information. An SAE occurring at a different time interval or otherwise considered completely unrelated to a previously reported one must be reported separately as a new event.

If the SAE is not previously documented in the IB or Package Insert (new occurrence) and is thought to be related to the study treatment, a Chief Medical Office & Patient Safety (CMO & PS) Department associate may urgently require further information from the investigator for health authority reporting. Novartis may need to issue an investigator notification (IN) to inform all investigators involved in any study with the same study treatment that this SAE has been reported.

Suspected unexpected serious adverse reactions (SUSARs) will be collected and submitted to the Competent Authorities and relevant Ethics Committees in accordance with EU Guidance 2011/C 172/01 or as per national regulatory requirements.

Any SAE occurring after the patient has provided informed consent and until the last study visit or 30 days after the last administration of study treatment whichever is later will be reported.

Any SAEs experienced after the above mentioned period should only be reported to Novartis Safety if the investigator suspects a causal relationship to study treatment.

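### The visit schedule does not guarantee the 30 days of adverse-event monitoring that protocol Section 10.1.1 requires for patients last treated at Week 44 or withdrawn from the study

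*Protocol*

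**What the plan says.** **Length of AE monitoring.** Protocol Section 10.1.1 states: "Adverse event monitoring should be continued until 30 days (safety follow-up) after the last administration of study treatment". The same sentence sends the reader to the post-treatment follow-up period in Section 3.

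**That period.** Section 3 heads it "Post-treatment follow-up period: from Week 40/44 to Week 48". For patients who complete per protocol, the end-of-study (EOS) "assessment will be performed at Week 48, 4 weeks (for patients treated at Week 44) or 8 weeks (for patients treated at Week 40"), plus or minus 7 days, counted as "following their last possible study treatment administration". Patients withdrawn before completion are asked back 4 weeks, plus or minus 7 days, after their last injection. Section 3 also says: "The maximum study duration for 1 patient is 48 weeks, including Screening".

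**Contacts outside visits.** Table 8-1 schedules nothing after Week 48. Its footnote 9 says: "A telephone follow-up on safety should be performed one week after the first injection". Calls after later injections are left to the investigator.

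**SAEs.** Section 10.1.3 requires reporting "until the last study visit or 30 days after the last administration of study treatment whichever is later".

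**Tabulation.** Protocol Section 12.5.2 ends the on-treatment period 30 days after the last injection. SAP Section 2.1.1 ends it after 28 days, and SAP Section 2.9.1 restricts the AE summary tables to that period. SAP Section 2.9.2 summarizes deaths to 30 days.

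**The concern.** Section 10.1.1 sets a 30-day requirement and points to a follow-up period that, after a Week 44 injection, is planned to last 28 days and may be shorter. AEs are to be sought by questioning at each visit. Once the EOS visit has taken place there is no further visit and no scheduled call at which anyone would ask.

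What is at stake is completeness of AE collection in the last days after the final injection. Intraocular inflammation, retinal vasculitis and retinal vascular occlusion prompted the protocol's safety amendments. An event of this kind that begins after an early EOS visit would come to light only if the patient reports it. The same holds for milder ocular and non-ocular events, which patients are less likely to volunteer.

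This is a question of whether events are collected. The difference between the 28-day and 30-day definitions is a related but separate question of which collected events enter a table.

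**Working it through.** **Inputs**
- EOS visit after a Week 44 injection: 4 weeks, window of 7 days either way (protocol Section 3).
- Required AE monitoring: 30 days (protocol Section 10.1.1).
- On-treatment period: 30 days (protocol Section 12.5.2) or 28 days (SAP Section 2.1.1).
- Scheduled days for Weeks 44 and 48: 308 and 336 (SAP Table 2-1).

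**1. The plan's own interval.** 336 − 308 = 28 days = 4 weeks. The stated figure is reproduced.

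**2. Range within the window.** 28 − 7 = 21 and 28 + 7 = 35, so the last scheduled contact falls on days 21 to 35 after the injection.

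**3. Shortfall.** Shortfall = max(required day − EOS day, 0).

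| EOS visit, days after last injection | Short of 30 days | Short of the SAP's 28 days |
|---|---|---|
| 21 (early limit) | 9 | 7 |
| 27 | 3 | 1 |
| 28 (nominal) | 2 | 0 |
| 29 | 1 | 0 |
| 30 to 35 | 0 | 0 |

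**4. Who has Week 44 as the last dose.** Patients on q12w throughout are treated at Weeks 8, 20, 32 and 44 after loading. Patients moved to q8w at Week 20 are treated at Weeks 20, 28, 36 and 44. Patients moved at Week 16 (16, 24, 32, 40) or at Week 32 (32, 40) end at Week 40. Their EOS visit is 336 − 280 = 56 days later, or 49 to 63 days with the window, so they are covered.

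**5. Patients who stop early.** Those withdrawn from the study have the same 21-to-35-day return and the same shortfall. Those who stop treatment but stay in the study are different: Section 9.1.1 keeps collecting their AEs, at visits or by telephone, at least to Week 48.

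**6. Another anchor.** Section 8 calculates visit dates from Day 1. If the Week 44 and Week 48 visits each move by 7 days independently, the interval between them runs from (336 − 7) − (308 + 7) = 14 days to (336 + 7) − (308 − 7) = 42 days. The shortfall could then reach 30 − 14 = 16 days. I do not rely on this reading, because Section 3 ties the EOS window to the last treatment.

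**The case against.** Much of the case on the other side stands.

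- **Serious events have their own rule.** Section 10.1.3 runs to the later of the last visit and day 30, so it already provides for a last visit before day 30. After that period, SAEs suspected to be related must still be reported. A reader might infer that SAEs in these days go unreported by design. The documents do not support that. What they lack is a scheduled contact through which the site would learn of such an event.
- **Ocular symptoms rely on self-report throughout.** Sections 8.4.3 and 10 tell patients to contact the site about changes in vision or symptoms of inflammation, and intervals between visits can be 12 weeks. This reduces the risk. However, the instruction is worded for the time between scheduled visits, and after EOS there is no next visit.
- **The requirement can be met.** An EOS visit on days 30 to 35 satisfies it, and no passage forbids a later call. A reader might infer that the 30 days are never delivered, that every patient last treated at Week 44 is affected, or that the 48-week maximum rules out day 30. The 7-day window contradicts all three.
- **The share of patients is unknown.** Nine of the 15 permitted days fall before day 30. It is tempting to read that as a proportion of patients, but this would need an even spread of visit dates. The documents give no distribution and ask sites to make all efforts to keep to the schedule.
- **The tables are less exposed than they look.** A reader might infer that the AE tables always present unasked days as event-free. Under the SAP's 28 days this can arise only for EOS visits on days 21 to 27. No planned AE table uses person-time either: adverse events of special interest are given per patient and per 1000 injections. The effect would be an unelicited event missing from the count, not an inflated denominator.

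What remains is that Section 10.1.1 relies on a period that is nominally too short, and nothing scheduled makes up the difference.

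**Conclusion.** The contradiction is real and small. For patients last treated at Week 44, and for patients withdrawn from the study, the visit schedule does not guarantee the 30 days of AE monitoring that the protocol states. The shortfall is 2 days on the nominal date, at most 9 days within the Section 3 window, and none for a visit on days 30 to 35. This rests on counting the window from the last injection, as Section 3 does. How many patients fall short cannot be derived from the documents.

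The loss concerns mainly events that patients do not report on their own, chiefly non-serious ones. Under the SAP's on-treatment definition the AE tables are affected only by final visits on days 21 to 27, with 1 to 7 counted days not asked about. Under protocol Section 12.5.2 they are affected by any final visit before day 30. The primary endpoint is untouched. The point still merits correction, because the protocol promises this follow-up, ocular inflammation is its main safety concern, and the remedy is cheap.

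**What to change.** Reconcile protocol Sections 3 (study duration and post-treatment period), 10.1.1, 10.1.3 and 12.5.2 with SAP Section 2.1.1, so that the monitoring period, the last scheduled contact and the on-treatment period agree. Where the final visit falls before day 30 after the last injection, add one telephone safety contact on or after day 30. It should take the form already used after the first injection, and it should be recorded in the eCRF; Section 8.4.3 currently asks only for source documentation of that first call. The call cannot apply to patients who have withdrawn consent, since Section 9.1.2 allows further contact with them only when safety findings require it.

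The cost is a short call for some patients, an eCRF entry, and a few sentences of amended text. No treatment rule or visit date changes.
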